3. AFTER-DISSECTION

A. Document visualization of extra-hepatic biliary anatomy:

For both arms, scope the Calot's triangle area using STD (white-light) mode. If in the NIFC arm, toggle between STD and ICG modes on light source as needed. Check the appropriate boxes below based on what is visible:

	Yes	Maybe	No
Cystic Duct			
Right Hepatic Duct			
Common Hepatic Duct			
Common Bile Duct (CBD)			
Cystic-CBD junction			
Cystic-Gallbladder junction			
Accessory Ducts			

B. For NIFC Arm Only: "Reflux Maneuver" Attempted? Yes No

Repeat the Reflux Maneuver. Check the appropriate boxes based on what is visible:

	Yes	Maybe	No
Cystic Duct			
Cystic-CBD junction			
Cystic-Gallbladder junction			

4. Time to Clip: Time the Cystic Duct was clipped: _____ AM / PM

5. Volume of Bleeding: _____ mL in the bucket/bag or from anesthesia chart at the conclusion of the procedure

6. Bile Leakage: No Yes If yes, Liver bed Other: _____ Did NIFC help identify leak? Yes No

7. Anatomic Anomalies: No Yes If yes, describe: _____

If yes, do you feel NIFC helped you identify this anomaly? Yes No N/A (WLI arm)

8. Was IOC performed? Yes No

9. Were CBD Stones present? Yes No Not Checked

10. Was the procedure converted to Open? Yes No

If yes, explain why: _____

11. Was there a Bile Duct Injury (BDI) during the surgery? Yes No

If yes, complete the BDI Form as described in the Study Protocol.

12. SURGEON FEEDBACK after NIFC:

Did you feel NIFC made your procedure SAFER? Yes No

Were you more CONFIDENT using NIFC vs WLI alone? Yes No

Would you PREFER to use NIFC again vs WLI alone? Yes No

e. Intra-Op Case Report Form – Observer

Near Infrared Incisionless Fluorescent Cholangiography (NIFC)

INTRA-OPERATIVE CASE REPORT FORM - OBSERVER

INSTITUTION: _____

PATIENT ID: _____

SURGERY PERFORMED BY: _____

PROCEDURE DATE: _____

OBSERVER NAME: _____
(PRINT)

(SIGNATURE)

EXPERIENCE LEVEL OF PERSON COMPLETING FORM:

ATTENDING (Years in practice ____) FELLOW RESIDENT (YR____) MEDICAL STUDENT (YR____)

ACADEMIC TITLE: _____ Approximate # of Lap Choles Performed: _____

STUDY ARM: **WLI** (STD mode on light source only) **NIFC** (using both STD and ICG modes)

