3. Compare the mean number of procedures that required Conversion to Open using NIFC vs WLI alone.
4. Compare the mean Volume of Bleeding using NIFC vs WLI alone.
5. Compare the Incidence rate of Bile Leakage from the liver bed using NIFC vs WLI alone.
6. Compare the Incidence rate of Bile Duct Injury (BDI) using NIFC vs WLI alone.
7. Compare the mean Surgeon Confidence Level using NIFC vs WLI alone.

5. Study Endpoints

a. Primary Endpoint:

Detection Rate (DR) of each particular extra-hepatobiliary structure during Laparoscopic Cholecystectomy (LC) defined as the total number of patients in which the particular structure is detected before and after dissection in that arm of the Study (WLI or NIFC), divided by the total number of patients in that arm. Extra-hepatobiliary structures to be included in this assessment: Cystic Duct, Right Hepatic Duct, Common Hepatic Duct, Common Bile Duct, Cystic-CBD junction, Cystic-Gallbladder junction, and any Accessory Ducts.

b. Secondary Endpoints:

1. The DR for students/residents only (apart from experienced surgeons), both before and after dissection.
2. Time to Clip
3. Incidence of Conversion to Open Surgery
4. Volume of Bleeding
5. Incidence of Bile Leakage from the liver bed
6. The mean Incidence of Bile Duct Injury (BDI)
7. Surgeon Confidence Level

6. Covariates

Besides the comparison of the outcomes in both study arms, we will conduct an exploratory analysis to identify potential effect modifiers. The following baseline variables will be considered:

- 1) Patient data:
 - a) Age
 - b) Gender
 - c) BMI
- 2) Patient history/condition:
 - a) obesity
 - b) liver disease
 - c) lithiasis
 - d) surgery status (elective/urgent/emergent)
- 3) Intra-operative factors:
 - a) amount of fat covering cystic artery
 - b) amount of inflammation
 - c) presences of adhesions / scar tissue
- 4) Surgeon expertise (resident/attendant)

7. Additional Observations (NIFC group only)

a. “Reflux Maneuver”

According to previous publications, in some cases the Cystic Duct may not be seen with NIFC because the Cystic Duct may not contain ICG at the time of viewing. In those cases, a “reflux maneuver” [defined as using an atraumatic laparoscopic instrument to push on the Common Bile Duct in order to move more of the ICG from the Common Bile Duct through the Cystic Duct into the Gallbladder – thereby increasing visualization of the Cystic-Gallbladder junction] can be performed.

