Upon entry in the clinical trial, the master study database (REDCap, described later in Section 16) will randomly allocated patients to one of the study arms (1:1) within site (1:1) using a computer generated random sequence. This will provide an allocation sequence for each site. Once a patient is enrolled and a database file in REDCap is initiated for that patient, he/she will be assigned electronically to one of the study arms.

Patient will be blind to the intervention but surgeon blinding will not be feasible due to the nature of the intervention. The study will involve a considerable number of surgeons in each site, which should compensate any potential bias of some of them in favor or against either approach.

e. Flow chart

Multi-center Study Protocol: Efficacy of Near Infrared Incisionless Fluorescent Cholangiography (NIFC) during Laparoscopic Cholecystectomy

[figure not shown]
Figure 1 shows the flow chart for the study, a multi-centered randomized controlled trial (RCT) 1:1 with two arms:

1. Control: WLI

A laparoscopic cholecystectomy will be performed using Xenon white light imaging (WLI) only.

2. Experimental: NIFC

A laparoscopic cholecystectomy will be performed using both white light imaging and near infrared light imaging with indocyanine green (ICG) intravenous dye.

9. Data collection and procedures

Data will be collected before, during and at the end of surgery; and one week after surgery.

a. Pre-Op data collection

i. Patient data

- Age
- Gender
- Weight
- Height
- BMI

ii. Patient clinical characteristics

- Liver disease
- Lithiasis
- Surgical status: elective/urgent/emergent

b. Intra-Op data collection

i. For NIFC arm only

- Time of ICC administration
- Was there any Adverse Reaction? If so, what happened and how was the patient treated?

ii. For both arms: PRIOR to dissection

- Categorize initial visualization
 - Amount of fat
 - Amount of inflammation
 - Presence of adhesions / scar tissue
- Remove the fat from the Calot's triangle area, retract the gallbladder and Hartmann's pouch
- Surgeon/Observer documents which extra-hepatic biliary structures are identified without doubt
- Start Dissection. Document the time hilar dissection was begun (baseline time)

iii. For both arms: AFTER dissection

- Surgeon/Observer documents which extra-hepatic biliary structures are identified without doubt
- Time to Clip: Document the time the Cystic Duct was clipped
- Volume of Bleeding
- Incidence of Bile Leakage

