<hr/> 
1. Length of hospital stay: _____ (days)
 
2. Was patient readmitted: No  Yes  If Yes, complete the following:
 
Days after discharge: _____ (NOTE: Day of Surgery is Day "0")Reason for readmission: _____Treatment administered: _____Length of stay: _____ (days) 
3. Death (30 d): No  Yes  If Yes, cause of death: _____
 
4. Complications: No  If No, you have completed this form. Yes  If Yes, please continue...
 
Indocyanine green drug reactions: No  If No, skip to surgical complications. Yes  If Yes, continue
Flushing? No  Yes  If yes, please complete:
Treatment required? No  Yes If Yes, what treatment: _____Urticaria? No  Yes  If yes, please complete:
Treatment required? No  Yes If Yes, what treatment: _____Other possible drug reaction? No  Yes  If Yes, please complete:
Describe: _____Onset (day of surgery is "0"): _____Duration (Hours): _____Treatment required? No  Yes If Yes, what treatment: _____ <hr/> 
MULTICENTER TRIAL
 
Page 1 of 2
 
POSTOP-CRF v1.0
		

Near Infrared Incisionless Fluorescent Cholangiography (NIFC)

2

POST-OPERATIVE FORM

b. Hemorrhage? No Yes If Yes, please complete:

- i. ... requiring transfusion? No Yes
- ii. ... requiring re-operation? No Yes
- iii. ... requiring longer hospitalization? No Yes

c. Intra-abdominal pain in right upper quadrant? No Yes

d. Bile leak (without bile duct injury)? No Yes If Yes, please complete:

- i. ... requiring percutaneous drainage? No Yes
- ii. ... requiring reoperation? No Yes
- iii. ... treated with percutaneous drainage only? No Yes
- iv. ... treated with transpapillary stent? No Yes
- v. ... treated with percutaneous drainage and transpapillary stent? No Yes

vi. Source of leak:

1. cystic duct stump leak? No Yes
2. liver bed? No Yes
3. never determined? No Yes

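### Objective 5 compares liver-bed bile leakage between arms, but intra-operative leaks may be found with fluorescence in the NIFC arm only, which biases that count against NIFC by an unknown amount

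*Combined protocol and SAP*

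**What the plan says.** Section 4.b, item 5, sets the objective: "Compare the Incidence rate of Bile Leakage from the liver bed using NIFC vs WLI alone". Section 5.b, item 5, makes it a secondary endpoint. Neither names a data source.

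Leakage is collected twice:

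- **During surgery.** Section 9.b.iii lists "Incidence of Bile Leakage" among the after-dissection data for both arms. Item 6 of the surgeon's form (Appendix d) records yes or no, the site (liver bed or other), and then asks "Did NIFC help identify leak".
- **After surgery.** Item 4.d of the post-operative form (Appendix f), which begins "Bile leak (without bile duct injury", is completed for both arms at about 7 to 10 days. Item 4.d.vi.2 offers the liver bed as the source.

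The arms differ in imaging (Section 8.e). For control, "A laparoscopic cholecystectomy will be performed using Xenon white light imaging (WLI) only". The experimental arm uses "both white light imaging and near infrared light imaging with indocyanine green (ICG) intravenous dye". Section 11.a says ICG is excreted through the biliary system. For the view after dissection, item 3.A of the surgeon's form says "If in the NIFC arm, toggle between STD and ICG modes on light source as needed"; that instruction concerns the duct anatomy around Calot's triangle. Section 8.d states that "surgeon blinding will not be feasible due to the nature of the intervention".

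Section 13.b names tests for bile duct injury, conversion to open surgery and bleeding. It names none for bile leakage and does not mention the answer to item 6.

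**The concern.** In one arm, the tool under test can also reveal the outcome event. Bile carrying ICG can be seen in ICG mode in the NIFC arm; a WLI patient has neither the dye nor the mode. The follow-up question on item 6 shows that the form's authors foresaw that NIFC might help find a leak. The plan contains no white-light-only leak reading in the NIFC arm, no common leak check for the two arms, and no analysis that uses the item 6 answer.

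If NIFC raises the chance that an existing leak is noticed, the intra-operative contrast mixes how often leaks occur with how often they are seen. Equal leak frequency could then look like harm, and a real reduction could shrink or vanish.

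**Working it through.** **No stated figure to reproduce.** The documents give no rate, effect size or power for bile leakage. The nearest figure (bile duct injury, 8/1000 against 2/1000, Section 13.a) concerns another outcome and is not used here.

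**Model for the intra-operative count.** Let Se be the probability that an existing leak is noticed during surgery.

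- Observed rate in an arm = true rate × Se in that arm.
- Observed risk ratio (RR) = true RR × (Se under NIFC ÷ Se under WLI).

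If Se is higher under NIFC, the factor exceeds 1 and the bias runs against NIFC. If Se is equal, there is no bias.

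**Inputs.** 500 patients per arm (Section 13.a). Everything else is assumed: true control leak rates of 1%, 2% and 4%, and the detection pairs below. The test is also an assumption: uncorrected chi-square, two-sided 5%, with exact enumeration of the two binomial counts.

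**Detection factor.** 0.90/0.90 = 1.00; 0.90/0.80 = 1.125; 0.95/0.70 = 1.36; 0.95/0.50 = 1.90.

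*No true difference (true RR 1):*

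| Se WLI / NIFC | Observed RR | Chance of significant harm at 1% / 2% / 4% |
|---|---|---|
| 0.90 / 0.90 | 1.00 | 2.1% / 2.4% / 2.5% |
| 0.80 / 0.90 | 1.125 | 3.2% / 4.1% / 5.2% |
| 0.70 / 0.95 | 1.36 | 5.4% / 8.5% / 13.8% |
| 0.50 / 0.95 | 1.90 | 11.4% / 20.7% / 39.7% |

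*True halving under NIFC (true RR 0.50):*

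| Se WLI / NIFC | Observed RR | Chance of significant benefit at 1% / 2% / 4% |
|---|---|---|
| 0.90 / 0.90 | 0.50 | 12.1% / 21.6% / 42.3% |
| 0.80 / 0.90 | 0.56 | 9.2% / 15.0% / 29.5% |
| 0.70 / 0.95 | 0.68 | 6.0% / 8.4% / 15.3% |
| 0.50 / 0.95 | 0.95 | 2.6% / 2.6% / 3.2% |

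In expected counts at a 2% true rate with 0.70/0.95: with no true difference, 500 × 0.02 × 0.70 = 7.0 leaks under WLI and 500 × 0.02 × 0.95 = 9.5 under NIFC. With a true halving, 7.0 against 500 × 0.01 × 0.95 = 4.75.

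**The post-operative count.** Let t be the proportion of leaks found and dealt with during surgery, and suppose these do not reappear. Then observed post-operative RR = true RR × (1 − t under NIFC) ÷ (1 − t under WLI), other things equal. If fluorescence raises t in the NIFC arm, this factor is below 1 and the post-operative count favours NIFC. That may be a genuine benefit of the strategy, but it does not measure how often leaks occur.

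**Pooling.** Pooling does not restore neutrality. A leak missed under WLI enters the pooled count only if it later becomes clinically apparent.

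**The case against.** Four points can be made for the plan.

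1. *No fluorescence leak search is prescribed.* A reader might infer from item 6 that surgeons in the NIFC arm look for leaks in ICG mode. The documents do not support that. ICG mode is used at discretion, to document ducts, and no imaging instruction mentions the liver bed. Item 7 asks a similar question about anatomic anomalies. What stands is that fluorescence *may* reveal a leak in one arm only, and that its use for this purpose is uncontrolled.

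2. *The endpoint is not tied to the intra-operative record.* This is correct. A post-operative record exists for both arms, and the documented gap is that the source is left open. That is a reason to fix the source, since nothing rules out the intra-operative or a pooled count.

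3. *The forms already hold much of the information.* This is also correct. Intra-operative and post-operative leaks are on separate forms, and a sensitivity analysis could omit leaks that NIFC helped identify. None is planned, however, and a leak that NIFC helped find might also have been seen in white light, so that analysis could over-correct.

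4. *The size is assumed and the comparison is weak anyway.* Even with equal 90% detection, a true halving reaches significance in only 12.1% to 42.3% of trials under the assumed rates. This stands, and it limits the importance of the point.

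A reader might also infer that Objective 5 cannot be interpreted in either direction. That goes too far: the bias from better detection has a known direction, so an observed reduction under NIFC in the intra-operative count would be conservative.

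**Conclusion.** The concern holds as a one-directional ascertainment bias in the intra-operative leak count. It rests on documented facts: the recorder is unblinded, only one arm has dye and near-infrared imaging, the form anticipates help from NIFC in finding leaks, and no analysis deals with this. To the extent that NIFC helps find leaks, a null or apparently harmful intra-operative result would be hard to interpret, whereas a reduction would be conservative. The latter assumes that detection under NIFC is no worse than under WLI and that unblinded recording does not itself favour NIFC.

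The size is unknown. Over the assumed detection pairs, a true RR of 1.00 is observed as 1.00 to 1.90, and a true 0.50 as 0.50 to 0.95.

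It is tempting to treat the post-operative count as the neutral replacement. It is not, because leaks dealt with during surgery can leave it unequally by arm.

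This is a secondary endpoint with no stated power, and this point does not affect the primary endpoint. The change is worth making because it is cheap.

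**What to change.** 1. **Name the source.** State which record Objective 5 uses, report intra-operative and post-operative leaks separately by arm without pooling them, and name the test.
2. **Reword item 6 of the surgeon's form.** Replace the question on NIFC help with two fields, *seen in white light* and *seen only in ICG mode*. Give the second a not-applicable option for the WLI arm, as item 7 already has. In the NIFC arm, the white-light field is answered before toggling. Base the intra-operative between-arm comparison on white-light leaks, and tabulate fluorescence-only leaks separately as a detection outcome.
3. **Report post-operative clinically apparent liver-bed leaks** (Appendix f, item 4.d.vi.2) as the clinical outcome of the whole strategy. Add a note that leaks found and dealt with during surgery can lower this count in the NIFC arm, so it is not a detection-neutral measure of leak occurrence.
4. **State where Type A injuries count.** Item 5 of the bile duct injury form (Appendix g) includes leaks from small liver-bed ducts in Type A, while item 4.d of the post-operative form covers leaks without bile duct injury. Without a rule, such events could be lost or counted under both Objectives 5 and 6.

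Cost: a few sentences in the analysis section and one changed form line. Each comparison will have fewer events, and the white-light reading still comes from an unblinded surgeon.

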	
4. Ability to understand and follow the study procedures and sign the informed consent
 
Exclusion Criteria
 
1. Known allergies to iodides2. Known history of cholangitis, pancreatitis, CBDS's, coagulopathy3. Known liver disease4. Women who are pregnant or breastfeeding, or for whom possibility of pregnancy was not ruled out 
1,000 patients enrolled across all centers
 
Male or female subjects undergoing laparoscopic cholecystectomy that fulfil all of the inclusion and none of the exclusion criteria.
 
Approximately 1 year
 
Primary Endpoints:
 
Detection Rate (DR) of each particular extra-hepatobiliary structure during Laparoscopic Cholecystectomy (LC) defined as the total number of patients in which the particular structure is detected before and after dissection in that arm of the Study (WLI or NIFC), divided by the total number of patients in that arm. Extra-hepatobiliary structures to be included in this assessment: Cystic Duct, Right Hepatic Duct, Common Hepatic Duct, Common Bile Duct, Cystic-CBD junction, Cystic-Gallbladder junction, and any Accessory Ducts.
 
Secondary Endpoints:
 
1. The DR for students/residents only (apart from experienced surgeons), both before and after dissection.2. Time to Clip3. Incidence of Conversion to Open Surgery4. Volume of Bleeding5. Incidence of Bile Leakage from the liver bed6. Incidence of Bile Duct Injury (BDI)7. Surgeon Confidence Level 
Test Device/Procedure:
 
Image1 SPIES (Storz Professional Image Enhancement System) Endoscopic ICG Imaging System
 
Comparator Device/Procedure:
 
Standard Image1 SPIES Endoscopic System using white light imaging (WLI) only
 
Statistical Analysis:
 
The DR (before and after dissection) between arms will be compared using the chi-square test while the number of

--	--

structures detected will be analyzed using non-parametric tests. Regression models (logistic or generalized mixed models) will be fitted to evaluate if the effect of NIFC on the primary outcomes is modified by the patient's or surgeon's characteristics or the site.

2. Introduction

a. Background

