- Incidence of Anatomic Anomalies of the extra-hepatic biliary system, including any Accessory Ducts
- Incidence of performing IOC
- Incidence of CBD stones
- Incidence of Conversion to open surgery
- Incidence of Bile Duct Injury (BDI)?

iv. For NIFC arm only

- PRIOR to and AFTER DISSECTION: Surgeon/Observer documents which extra-hepatic biliary structures are identified without doubt using the "Reflux Maneuver" during NIFC
- Was the "reflux maneuver" useful?
- Surgeon preference: Was NIFC helpful?

c. One-week Post-Op data collection (usual control after surgery)

- Length of hospital stay

- Readmission?
- Complications?
 - Adverse drug reactions
 - Hemorrhage
 - Bile leak
 - Bile duct injury
- Death?

10. Subject Selection

a. Inclusion Criteria

1. Patients of both genders
2. Minimum age: 18 years old
3. Spoken and written command of the language spoken in the country's center
4. Ability to understand and follow the study procedures and sign the informed consent

b. Exclusion Criteria

1. Known allergies to iodides
2. Known history of cholangitis, pancreatitis, CBDS's, coagulopathy
3. Known liver disease
4. Women who are pregnant or breastfeeding, or for whom possibility of pregnancy was not ruled out

11. Study Device

a. Indocyanine Green (ICG) Fluorescent Dye

The drug used in these studies to evaluate the extra-hepatic bile duct is indocyanine green (ICG) and the equipment uses a wavelength around 800 nm (32,33,34,35,36,37). ICG, a cyanine dye, has been used in various medical diagnostic procedures since its FDA approval in 1956 (38).

ICG is a fluorophore responding to near-infrared irradiation that absorbs light between 790 and 805 nm, and re-emits it with an excitation wavelength of 835 nm. When given intravenously, ICG binds to plasma proteins and becomes confined to the intravascular space [15]. It is then exclusively metabolized by the liver and excreted by the biliary system 15 to 20 minutes after administration. These properties, in conjunction with the absence of any native biological fluorescence within these wavelengths, make ICG an ideal agent for the acquisition of high-quality images of the biliary tract.

b. Equipment

KARL STORZ (Tuttlingen, Germany) has developed a laparoscopic fluorescence imaging system that is suitable for both near-infrared fluorescence and xenon

Multi-center Study Protocol: Efficacy of Near Infrared Incisionless Fluorescent Cholangiography (NIFC) during Laparoscopic Cholecystectomy

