c. Patient Randomization

Each surgeon will follow the standard laparoscopic surgical protocol of his/her center, and will comply with the following additional steps according to which arm of the study the patient is assigned:

i. Control arm (WLI only) procedures

1. After inserting the scope in the abdominal cavity, once other standard operatory procedures (e.g., taking down adhesions if necessary, or releasing scar tissue) are completed using white light imaging (WLI) only, the Researcher will record the time when Calot's triangle is first visualized. From this moment on, the surgery will be recorded.
2. After removing the fat from the gallbladder area, lifting the gallbladder over the liver, and grabbing the Hartman's pouch to visualize the Calot's triangle, but PRIOR TO DISSECTION, the Researcher will determine what extra-hepatic biliary structures can be specifically identified. Of note: because one of the goals of the Study is to evaluate NIFC as a teaching tool, residents and juniors should record what structures they were able to identify by themselves before any intervention of the attendant surgeon.
3. Then, AFTER DISSECTION, a similar assessment of what extra-hepatic biliary structures can be specifically identified using WLI only will be performed.
4. Anatomic anomalies of the biliary system will be documented on the case form and if an anatomic variation is found, a snap shot photo will be taken in addition to the video.
5. Immediately before clipping or proceeding with open surgery, the total time from Step 1 will be recorded, known herein as the "Time to Clip";

6. Before leaving the operation room, all participant surgeons and observers will complete the Intra-Operative Case Report Form (Appendices D and E, respectively).

ii. Experimental arm (NIFC) procedures

1. Patient randomized to the experimental arm, at least 45 mins before surgery, will receive a weight-scaled dose of indocyanine green (0.05 mg/kg) by IV and the time of administration and any adverse reactions will be recorded.
2. After inserting the scope in the abdominal cavity, once other standard operatory procedures (e.g., taking down adhesions if necessary, or releasing scar tissue) are completed using white light imaging (WLI) only, the Researcher will record the time when the Calot's triangle is first visualized. From this moment on, the surgery will be recorded.

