Regarding the main secondary outcome, incidence of injuries, the power to detect a drop from 8/1000 in the control arm to 2/1000 in the intervention arm, with a sample size of 500 patients per arm is 15%. Regretfully, with an achievable sample size as the one proposed above, the study will not have enough power to detect a drop in the incidence as important as the one considered.

b. Data Analysis

In general, descriptive statistics including frequencies and means will be used to characterize patient's baseline characteristics in both study arms. Analyses are designed to test the following hypotheses based on the primary objectives: Compared to those in the control arm, surgeons using NIFC will be able to identify a) more frequently the gallbladder cystic union (both before dissection and before clipping); b) a larger number of hepato-biliary structures and; c) more frequently some of the five hepato-biliary structures. We will test the first hypothesis using the chi-square test, the second one using non-parametric test (e.g. Kruskal-Wallis) and the third one using generalized mixed or hierarchical models to account for the clustering induced by the patient.

Multi-center Study Protocol: Efficacy of Near Infrared Incisionless Fluorescent Cholangiography (NIFC) during Laparoscopic Cholecystectomy

Regression models (logistic or generalized mixed models) will be fitted including covariates to evaluate if the effect of NIFC on the primary outcomes is modified by the patient's or surgeon's characteristics and site.

Regarding secondary outcomes we will use the Fisher's exact test or Chi square test (as needed) to compare proportion of patients with bile duct injury, open surgery or bleeding. Time to clipping and time to end of surgery will be compared between arms using the Kruskal-Wallis' test. Regression models will be used when possible -we expect very low incidence of injuries and open surgeries- to evaluate patient's and surgeon's effect modification.

Finally, for those outcomes specific for the NIFC group we will use logistic or generalized linear models to assess whether the reported helpfulness of the NIR light or the reflux maneuver is associated to patient's characteristics or surgeon's experience.

All statistical analysis will be conducted in R software.

14. Anticipated Problems and Solutions

a. Lower than expected Enrollment

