2. PRE-DISSECTION

A. Categorize the initial visualization:

- Amount of fat: Can you see the Cystic Artery? Yes No
- Level of inflammation: Minimal Moderate Significant
- Were adhesions and/or scar tissue needed to be removed prior to visualization? Yes No

B. Remove the fat from the Calot's triangle area, retract the gallbladder and Hartmann's pouch.

C. Document visualization of extra-hepatic biliary anatomy:

For both arms, scope the Calot's triangle area using STD (white-light) mode. If in the NIFC arm, toggle between STD and ICG modes on light source as needed. Check the appropriate boxes below based on what is visible:

Time of Initial Visualization: _____ AM / PM

	Yes	Maybe	No
Cystic Duct			
Right Hepatic Duct			
Common Hepatic Duct			
Common Bile Duct (CBD)			
Cystic-CBD junction			
Cystic-Gallbladder junction			
Accessory Ducts			

D. For NIFC Arm Only: "Reflux Maneuver" Attempted? Yes No
If the Cystic Duct cannot be visualized with fluorescence, use anatraumatic laparoscopic instrument to push on the Common Bile Duct in order to move more of the ICG from the Common Bile Duct through the Cystic Duct into the Gallbladder – thereby increasing visualization of the Cystic Duct - Gallbladder Union. Check the appropriate boxes based on what is visible:

	Yes	Maybe	No
Cystic Duct			
Cystic-CBD junction			
Cystic-Gallbladder junction			

MULTICENTER TRIAL

Page 1 of 2

SURG-CRF v1.0

Multi-center Study Protocol: Efficacy of Near Infrared Incisionless Fluorescent Cholangiography (NIFC) during Laparoscopic Cholecystectomy

Near Infrared Incisionless Fluorescent Cholangiography (NIFC)
INTRA-OPERATIVE CASE REPORT FORM - PERFORMING SURGEON

START DISSECTION: Time of hilar dissection: _____ AM / PM

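### Secondary objective 7 promises a comparison of surgeon confidence between NIFC and WLI, but confidence is asked only as a Yes/No opinion about NIFC, so the WLI arm supplies no value to compare

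*Combined protocol and SAP*

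**What the plan says.** - **Objective.** Item 7 of the secondary objectives (Section 1 Summary and Section 4.b) reads "Compare the mean Surgeon Confidence Level using NIFC vs WLI alone".
- **Endpoint.** Item 7 of the secondary endpoints (Section 1 Summary and Section 5.b) is only the name, "Surgeon Confidence Level". It gives no scale, rater or time of assessment.
- **Form.** In Appendix D (Intra-Op Case Report Form – Surgeon), item 12 is headed "SURGEON FEEDBACK after NIFC". It has three Yes/No lines, and the one on confidence is "Were you more CONFIDENT using NIFC vs WLI alone". The pre-operative, observer, post-operative and bile duct injury forms have no confidence item.
- **Data list.** Section 9 lists no confidence variable for either arm. Its surgeon-opinion entries are whether the reflux maneuver was useful and "Surgeon preference: Was NIFC helpful", both in Section 9.b.iv, which covers the NIFC arm only.
- **Analysis.** For secondary outcomes, Section 13.b names Fisher's exact or chi-square tests "to compare proportion of patients with bile duct injury, open surgery or bleeding", and Kruskal-Wallis tests for two times. Its closing paragraph plans models within the NIFC group for the reported helpfulness of the near-infrared light or the reflux maneuver. Confidence appears in none of these.

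**The concern.** A difference between arms needs the same quantity measured in both. Here the plan declares the comparison, but its only instrument asks the surgeon to make that comparison personally, after using NIFC. A surgeon in the control arm has used white light alone and has nothing to answer.

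Two things are at stake. One of seven declared secondary objectives would end without a randomized result, and the missing WLI ratings cannot be recovered once the operation is over. The item 12 answers might also be reported in place of the objective. That would present an opinion from surgeons who knew they were using the new system as though it were a trial comparison.

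**Working it through.** The plan gives no effect size, standard deviation or power for this endpoint, so there is no figure to reproduce. The check is mainly structural.

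**1. Is a between-arm contrast intended?** Objectives 2 to 6 use the same NIFC-versus-WLI-alone phrasing for time to clip, conversion, bleeding, bile leakage and bile duct injury. All of these are arm comparisons. Objective 7 follows the same pattern.

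**2. How many values does each arm supply?** Allocation is 1:1 (Section 8.d) and Section 13.a works with 500 per arm.
- NIFC arm: up to 500 Yes/No answers to item 12.
- WLI arm: 0 usable answers.

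The standard error of a difference in means is SD × √(1/n_NIFC + 1/n_WLI). With n_WLI = 0 it is undefined, and the same holds for a difference in proportions.

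**3. What can be estimated?** Only the NIFC-arm proportion answering Yes. The 95% half-width is 1.96 × √(p(1 − p)/500), treating answers as independent:

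| True proportion | Half-width (percentage points) |
|---|---|
| 50% | 4.4 |
| 70% | 4.0 |
| 80% | 3.5 |
| 90% | 2.6 |

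Repeated answers from the same surgeon widen this. As an illustration, assume 50 surgeons with 10 cases each and an intraclass correlation of 0.05 to 0.20. The design effect 1 + 9 × ICC is then 1.45 to 2.80, and 4.4 points becomes about 5.3 to 7.3.

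**4. What would a rating in both arms give?** Assume one independent numeric rating per patient, 500 per arm, and a rank test with efficiency 0.955 relative to the t-test (its value under normality). The difference detectable with 90% power, in SD units, is (z_α + 1.2816) × √(2/500) / √0.955.
- One-sided 5% (the convention Section 13.a states for detection rates): (1.645 + 1.2816) × 0.0632 / 0.977 = 0.189 SD.
- Two-sided 5%: (1.960 + 1.2816) × 0.0632 / 0.977 = 0.210 SD.

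The documents give no SD. On an assumed 0–10 scale:

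| Assumed SD (points) | One-sided 5% | Two-sided 5% |
|---|---|---|
| 1.5 | 0.28 | 0.31 |
| 2.0 | 0.38 | 0.42 |
| 2.5 | 0.47 | 0.52 |

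These figures size the remedy. The finding rests on steps 1 and 2.

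**The case against.** The strongest reply is that objective 7 never says between arms. Surgeons in the NIFC arm toggle between white light and fluorescence in the same operation, so item 12 can be read as the intended within-operation comparison, and the gap becomes one of wording. This is a possible reading, but it gives objective 7 a different meaning from the five objectives before it that share its phrasing. If it is what was meant, the objective still has to be restated.

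Other points have some force:

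- **The word mean is used loosely.** The protocol also applies it to conversions and to bile duct injury, which are binary, and endpoint 7 does not use it. A Yes/No item could be summarised as a proportion. The missing WLI measurement is the decisive fault.
- **Item 12 is not marked as NIFC-only.** A surgeon in a WLI case could tick a box, but the answer would not describe confidence in that operation. Item 7 of the same form provides a not-applicable choice for the WLI arm; item 12 does not.
- **Both arms complete Yes/Maybe/No grids.** These carry some information on certainty. However, the instruction is "Check the appropriate boxes below based on what is visible", they feed the detection rate, and nothing defines them as confidence. Adopting them later would create a post hoc endpoint from the primary endpoint's data.
- **Section 13.b foresees opinion analyses within the NIFC group.** That is a natural place for item 12, but those models give no contrast between arms and do not name confidence.
- **A new rating would also come from unblinded surgeons.** This stands. Randomization would make the groups comparable but would not remove reporting bias.

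**Conclusion.** The concern holds. Followed exactly, the plan cannot estimate the comparison in secondary objective 7: about 500 of 1,000 patients have no usable confidence value, and only a descriptive NIFC-arm proportion remains. This conclusion needs no numerical assumption beyond the planned 500 per arm. The precision and detectable-difference figures depend on independent ratings, and the figures in points also on an assumed scale and SD.

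The reach is limited to one subjective secondary endpoint for which no power is claimed, and the primary detection-rate conclusion is unaffected. It should still be corrected before enrolment, because the data cannot be collected afterwards.

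A minor related mismatch: Section 13.b also compares the time at which surgery ends, which is not a listed endpoint and has no field on any form or in Section 9.

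**What to change.** 1. Add one confidence rating on a defined numeric scale (for example 0–10) to the surgeon form. The performing surgeon should complete it at the same point in both arms, before the NIFC feedback block. List it in Section 9.b for both arms and define it in endpoint 7.
2. Add a line to Section 13.b naming the between-arm test, for example a rank test, with an analysis that allows for clustering by surgeon. Make the word mean in objective 7 agree with that test. State that the ratings are unblinded.
3. Report the present item 12 line descriptively, as NIFC-arm opinion.
4. If no rating is wanted, restate objective 7 and endpoint 7 as a description of the NIFC arm.
5. For the related mismatch, add an end-of-surgery clock time with a defined start point, or delete that comparison from Section 13.b.

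The cost is small. Under Section 12.c, in each arm "all participant surgeons and observers will complete the Intra-Operative Case Report Form" before leaving the operating room, so the main change is one extra item on an existing form, with the matching definition and analysis line. Option 4 changes wording only.
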